Reported side effects for FDA-approved prescription medications differ from those reported for over-the-counter oral supplements. For example, the FDA-approved intravenous formulation of NAC has a side effect of prolonged bleeding (delayed blood clotting). However, this side effect has not been reported for the dietary supplement of NAC. Other side effects related to prescription formulations of NAC, especially those that are intravenous, inhaled or injected, may be found in the literature and on the internet, but may not be applicable to the dietary supplement utilized in this study. Participants are informed that they may find information about side effects related to NAC, which may in fact only be related to other prescription formulations of the drug. Participants are expected to inform study investigators about any concerns they have regarding side effects for NAC found in outside sources.

In a pediatric study by Tirouvanziam et al. (2006), 18 patients took the approximate dose in our proposed study using the same administration we plan to use (PharmaNAC effervescent tablets). 7/18 of these patients had mild symptoms of heartburn (4 patients), bad taste (1 patient), flatulence (1 patient), and nausea (1 patient). None of these symptoms required clinical monitoring. In another pediatric study by Hardan et al (2012) also using the PharmaNAC effervescent tablets, but through a higher dose range, thirty-three subjects (31 male subjects, 2 female subjects; **aged 3.2–10.7 years**) were randomized to receive NAC or placebo for 12 weeks. Subjects were initiated on NAC at **900 mg daily for 4 weeks, then 900 mg twice daily for 4 weeks and 900 mg three times daily for 4 weeks**. This was a 12-week double blind, randomized, placebo-controlled trial in children with autistic disorder. Based on the result of the study, NAC resulted in significant improvements on an irritability subscale compared to placebo. The most common adverse effects observed during the study were gastrointestinal and included nausea/vomiting, constipation, increased/decreased appetite and diarrhea (Hardan et al., 2012). We expect the same side effects in our pediatric population given that NAC is a precursor to the endogenous antioxidant GSH. We do not suspect any specific side effects in myopathies given this mechanism of action.

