In our proposed study, after participants receive drug or placebo effervescent tablets at the 6-month visit, they will be monitored at NIH for 2 consecutive days as an extra precaution to rule out rhinorrhea, stomatitis, urticarial/ facial flushing, rash, pruritus, hives, coughing, headache, drowsiness, clamminess, chest tightness, bronchoconstriction, and hypotension, which are the most severe potential side effects of inhaled or injected NAC. This monitoring will include being observed in the outpatient clinic for 2 hours after their initial dose, including having vitals signs measured. The second day of observation at NIH will include an outpatient clinic visit with vital signs. If at any other time, the participant notices any symptoms, they will be directed to contact our onsite nurses. A Licensed Care Provider will then call them at one and three weeks to monitor adverse reactions. We will then monitor participants monthly (2, 3, 4, and 5 months) by phone and/or email, primarily for gastrointestinal symptoms, which are the main symptoms of PharmaNAC effervescent tablets. If a patient reports any of the side effects that have already been reported (rash, chest tightness with coughing, hives, or hypotension), they will be advised to stop taking the study medication immediately. They will only restart the study medication after discussing their symptoms with the PI. Patients are also asked, in the consent form, to limit their alcohol consumption to no more than 2 alcoholic drinks per day as excess alcohol consumption may interact with glutathione levels. Participants are informed to call study investigators immediately if they have any problems or side effects and are provided with contact information. They are instructed to visit the emergency room if they have a possible allergic reaction or a serious or life-threatening emergency. They are expected to tell the ER staff that they are in a research study and ask the emergency personnel call the research nurse. Participants are instructed to continue under the care of their local clinicians throughout participation. Participants are provided with a “NAC Information Letter for Clinicians” (Appendix F) to share with their home clinicians. This letter provides study drug information and information about possible side effects.

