The telephone consent process described above may be used to obtain written re-consent from participants who are already enrolled. Written informed consent will be obtained from minor participants when they reach the age of consent for continued use of their samples or data. The telephone consent procedure detailed above may be used for such consent.

For NIH employees: Consent may be obtained by a co-worker. If so, independent consent monitoring will be provided by the NIH HSPU.

c. Consent documents

The consent contains all required elements. The consents attached to the protocol include adult patient and healthy volunteer populations (or parent of minor participants) and two different minor assents (ages 7-13 and 14-17), both for patients and healthy volunteers.

15. Data and Safety Monitoring

An independent monitoring committee will be put into place for Phase 2 of the study, including three experts in the field of neurology.

This committee will meet once every 3 months after the start of Phase 2 and is comprised of:

[name], PhD, NIAMS, Muscle Disease Unit Leader, specializes in patients with myositis and autoimmune toxic myopathies and muscular dystrophies.

[name], University of Toronto, is the Chief of Clinical and Metabolic Genetics at the Hospital for Sick Children and specializes in neuromuscular diseases.

[name], University of Indiana, Professor of Nursing at U. Indiana and specializes in pediatric epilepsy and chronic illnesses in children. She has served on Data and Safety Monitoring Boards for 2 national trials and a number in Indiana.

a. Data and safety monitor

This study will be monitored by the PI for Phase 1 of the study and by an independent monitoring committee for Phase 2.

b. Data and safety monitoring plan

Parameters to be monitored include liver function tests at the baseline visit and gastrointestinal symptoms throughout the 2nd phase of the study.

Liver Function Testing (LFT) in patients with RYR1-RM: LFTs are often elevated in our patient population. In patients with neuromuscular disease, the following criteria must be met, in order to determine impaired liver function. These guidelines will be used for determining impaired liver function in patients with RYR1-RM.

Evidence of moderate to severe hepatic involvement in this patient population is defined as:

ALT \geq 8x upper limit of normal (ULN) with total bilirubin 2x ULN (plus >35% 'direct' bilirubin) and/or INR >1.5

or

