Date: July 2, 2018

RE: Statistical Analysis Plan for Protocol 15-NR-0072 Antioxidant therapy in RYR1-related congenital myopathy

Primary outcome measures

Where to find data (variables) for the below analyses in locked excel files:

- 1) AE_Spreadsheet_Demographics_LOCKED_2018.3.29
- 2) Urinelsoprostane_6MWT_LOCKED_2018.3.29
- 3) PillCount_PlasmaRedox_SalivaFBI_SMOxidativeStressDCFH_LOCKED_2018.3.29

Descriptive statistics

- Assess data distribution (i.e. basic descriptive statistics) for demographics (sex, ethnicity, smoking_status, alcohol_consumption, age_month0, height_month0, weight_month0, bmi_month0)

- Assess data distribution for urine isoprostane (all variables)

- Assess data distribution for six-minute walk test (predicted_distance_walked_month0, min_6_distance_month0, predicted_distance_walked_month6, min_6_distance_month6, predicted_distance_walked_month12, min_6_distance_month12).

- Assess data distribution for skeletal muscle oxidative stress (all variables),

- If possible, also assess data distribution for plasma redox (GSH_GSSG_month0, GSH_GSSG_month6, GSH_GSSG_month12, CYS_CYSS_month0, CYS_CYSS_month6, CYS_CYSS_month12).

- Assess data distribution for pill count (percent_compliance_month12).

- Descriptive statistics (frequency, mean, median, SD, SEM, IQR, range) for all the above for entire cohort at baseline (month 0) for demographics.
- Repeat abovementioned descriptive statistics split by treatment group (NAC and placebo) at baseline.
- Assess the frequency of AEs by system organ class (System Organ Class (SOC) (AE only) and by Preferred Term (Preferred Term (AE only)).

Natural history phase analyses

During the natural history phase of the study (month 0 to month 6), we will take one look at the data prior to the final analysis with the following two approaches:

1. After 30 participants complete their baseline visit, we will compare their baseline outcome measure values against healthy controls. The mean values for the primary outcome measures (corrected 15-F2t-isoprostane concentration and 6MWT distance) will be compared against existing data for otherwise healthy individuals using summary independent t-tests and/or standardized mean difference (i.e. Hedge's g which is a measure of effect size between two means, weighted by n). This analysis will be repeated when all baseline visits are completed.

Null Hypothesis (H_0)

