2. UP/SAE
3. Non-UP/SAE

The other categories do not apply as they are not AEs.

Please use these categories in column F: "IRB determination of category".

Exclude HVs (healthy volunteers) and only use RYR numbers. Exclude RYR023 and RYR024.

For the remaining AE events (i.e. in the 3 categories delineated above) all have individual RYR IDs.

Assess:

1. Which AEs occurred in NAC group and which occurred in Placebo group (descriptive statistics) (see attached p.1 Mock Table 1)

2. Were there more specific AEs (by preferred term, Column H on excel) of any kind in NAC vs. Placebo groups? Or were AEs equally distributed between groups? Both Chi-square test and Fisher's exact test extended to general RxC tables, aka the Freeman-Halton test, will be used to compare AE frequencies between NAC and Placebo groups.
3. For those in NAC group, what was event causality (see AE excel column Q) and what was event severity (AE excel column R)? (for an example of this table, see p. 7 of attached, first table on p. 7). Capture the "body system" from our AE excel column G (AKA "system organ class").

Secondary Outcome Measures

Natural History Phase (month 0 to month 6):

Aim 1: plasma GSH:GSSG ratio; plasma CYS:CYSS ratio, (corrected DCF-fluorescence intensity (month 6 only))

1. We will compare baseline outcome measure values against healthy controls, when possible, using a summary independent t-test (or non-parametric equivalent). Hedge's g will be used to assess standardized mean differences between *RYR1*-RM and otherwise healthy population groups.

Null Hypothesis (H_0)

There will be no difference in mean plasma GSH:GSSG ratio; plasma CYS:CYSS ratio, or corrected DCF-fluorescence intensity, between *RYR1*-RM and otherwise healthy individuals.

Alternative Hypothesis (H_1)

Plasma GSH:GSSG, and CYS:CYSS ratios will be significantly decreased and corrected DCF-fluorescence intensity will be significantly increased in *RYR1*-RM myopathy patients when compared to otherwise healthy individuals.

2. We will compare baseline outcome measure values against values obtained at month 6 using paired t-tests (or non-parametric equivalent) to determine changes between 0 and 6-month visits for each outcome measure.

Null Hypothesis (H_0)

Plasma GSH:GSSG, and CYS:CYSS ratios and corrected DCF-fluorescence intensity will not change significantly between 0 and 6 months in *RYR1*-RM myopathy patients.

Alternative Hypothesis (H_1)

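### The SAP states no NAC-versus-placebo comparison of gastrointestinal events as a class, although the protocol expects and monitors that class; its stated test is framed by preferred term

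*SAP*

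**What the plan says.** **Expected harm.** Protocol section 7 lists six gastrointestinal side effects of the effervescent tablets: nausea, vomiting, diarrhoea, constipation, abdominal pain and flatulence. It directs the monthly contacts in Phase 2 "primarily for gastrointestinal symptoms, which are the main symptoms of PharmaNAC effervescent tablets". Section 15(b) names as monitored parameters baseline liver function tests and "gastrointestinal symptoms throughout the 2nd phase of the study". In both places the symptoms are handled as one group.

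**Prior rate.** Section 7 also cites an 18-patient series on about the same dose of the same product: "7/18 of these patients had mild symptoms of heartburn (4 patients), bad taste (1 patient), flatulence (1 patient), and nausea (1 patient").

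**Between-arm analysis.** Item 2 of the SAP's Adverse Event Analysis asks "Were there more specific AEs (by preferred term, Column H on excel) of any kind in NAC vs. Placebo groups", and then "Or were AEs equally distributed between groups". It answers with a chi-square test and Fisher's test "extended to general RxC tables, aka the Freeman-Halton test, will be used to compare AE frequencies between NAC and Placebo groups". Item 1 is a descriptive listing by arm that points to a mock table not included in the documents.

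**Use of system organ class.** It appears twice. Descriptive statistics has "Assess the frequency of AEs by system organ class (System Organ Class (SOC) (AE only) and by Preferred Term (Preferred Term (AE only"), with no mention of arm. Item 3 asks "For those in NAC group, what was event causality (see AE excel column Q) and what was event severity (AE excel column R") and takes the body system from column G, so it has no comparator.

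**The concern.** The protocol watches a class of symptoms, and the SAP tests its components. If NAC raises gastrointestinal complaints generally, the affected patients are spread over several preferred terms, each with few cases. A test framed at that level can return no significant result while the class as a whole is in excess. Item 2 offers equal distribution between the arms as the alternative answer, so a null result could be read as evidence of comparable tolerability on the effect the protocol most expects. No class-level estimate or interval is specified that would correct that reading.

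**Working it through.** **Arm size.** The AE section gives none, so I use the 38 per group in protocol section 10(b). Reproducing that figure (glutathione change 1.7 v 0, SDs 2.34 and 2.80, two-sided 0.05, 80% power):

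- Normal approximation: n = (2.34² + 2.80²)(1.96 + 0.84)² / 1.7² = 13.32 × 7.85 / 2.89 = 36.2, so 37.
- Satterthwaite t-test with noncentral t: n = 38, power 80.9%. The plan's figure is reproduced.

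Section 3(a) targets 76 completers, which matches 38 per arm. (Section 10(b) also says 76 per group, which conflicts; nothing here depends on it.)

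**Event rates.** NAC, from the 18-patient series: heartburn 4/18 = 22%, nausea 1/18 = 6%, flatulence 1/18 = 6%, any gastrointestinal event 6/18 = 33% (bad taste left out). No placebo rate is given, so I assume 5 to 20% for the class and scale each term in proportion. At 10%, for example, heartburn on placebo is 22% × 0.10/0.333 = 6.7%.

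**Power of a 2×2 comparison of patients.** This is the sum over all (x, y) of Bin(x; 38, p_NAC) × Bin(y; 38, p_placebo), counting tables with two-sided Fisher p ≤ 0.05. The 0.05 level is an assumption, since the AE section states none.

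| Placebo, any GI (assumed) | Any GI event | Heartburn alone | Nausea or flatulence |
|---|---|---|---|
| 5% | 88% | 60% | 1.3% |
| 10% | 63% | 38% | 1.0% |
| 15% | 38% | 21% | 0.7% |
| 20% | 19% | 11% | 0.5% |

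**Smaller arms.** Any GI event, 33% v 10%: 49% at 30 per arm and 32% at 20.

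**Why single terms do badly.** With no placebo cases, a term needs 6 NAC cases to reach 0.05 (6 v 0, p = 0.025; 5 v 0, p = 0.054).

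**Illustration.** Take any GI event in 14/38 v 5/38.

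- Fisher p = 0.032.
- Risk difference = 36.8% − 13.2% = 23.7 points from unrounded values. SE = √(0.368×0.632/38 + 0.132×0.868/38) = 0.0956, so the simple 95% CI is 5.0 to 42.4 points.
- The same patients split over six terms as 4 v 1, 3 v 1, 2 v 1, 2 v 1, 2 v 1 and 1 v 0 give p = 0.36, 0.61, 1, 1, 1 and 1.

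**One table of all terms by arm.** The SAP names RxC tests, so separate 2×2 tests may not be what it intends. A simulation of a single table (1,500 trials per scenario; each affected patient has one GI term; 10 to 30 background non-GI terms and 0.5 to 2 background events per patient, all assumed) gave, for 33% v 10%:

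| Pattern of GI terms | Class test | Any GI term with Fisher p < 0.05 | Freeman-Halton, whole table | Chi-square, whole table |
|---|---|---|---|---|
| Six equal terms | 62–64% | 5–6% | 10–13% | 5–7% |
| Clustered 4:1:1, as in the series | 63% | 40% | 18% | 10% |

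The class comparison has the highest power under either reading of item 2. A table of event counts also compares the mix of terms, not how many patients are affected. When all events were raised about 2.6-fold on NAC, it rejected in only 4 to 5% of simulations.

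**The case against.** Several objections have force.

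- **The level of the test is not fully fixed.** Only the first question in item 2 mentions preferred terms; the follow-up question and the test sentence name no level. This stands as an ambiguity, but no class-level comparison is stated either way.
- **An excess would not be hidden.** Item 1 sets out events by arm and system organ class is tabulated. The unseen mock tables may cross class with arm. A reader might infer that the SAP conceals gastrointestinal harm; the documents do not support that.
- **The true excess may be small.** Protocol section 1 reports that in a placebo-controlled paediatric trial side effects were gastrointestinal but did not differ significantly between arms. The 33% comes from 18 patients with no placebo rate reported. At 20% on placebo the class test itself has only 19% power.
- **Arms may be smaller than 38.** Section 10(b) says the recalculated N of 182 was not feasible and the study is being closed to data analysis. The number randomised is not given.
- **Heartburn dominates the cited series.** At 5% on placebo it alone has 60% power, so an excess would more likely than not show up at term level.

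Together these rule out the stronger inference that a real excess would probably be reported as balanced. It also goes too far to call gastrointestinal symptoms the only known harm: the protocol calls them the main symptoms, monitors liver function, and gives instructions for rash, chest tightness, hives and hypotension. What remains is that the class comparison is at least as informative in every scenario examined, and it is not specified.

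**Conclusion.** The point holds in a limited form. The SAP states no NAC-versus-placebo comparison for the class of events the protocol expects, and framing the test by preferred term gives up power. At an assumed 10% placebo rate and 38 per arm, power is 63% for the class, 38% for the commonest single term and about 1% for the others; one table of all terms gives roughly 5 to 18%. A gastrointestinal excess could therefore be missed.

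These sizes rest on the 18-patient series, assumed placebo rates, a planning arm size, a 0.05 level and, for the single table, assumed background events. In small arms or with a high placebo rate the class test is weak too, so the interval matters more than the p-value. This is a worthwhile improvement to the safety analysis and does not bear on the primary efficacy result.

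**What to change.** In SAP Adverse Event Analysis, item 2, add a NAC-versus-placebo comparison of the proportion of patients with at least one gastrointestinal event (column G) during the treatment phase. Count each patient once, and report the risk difference with its 95% CI and Fisher's exact test. Keep the preferred-term table as descriptive detail, and do not read a non-significant term-level test as showing equal distribution. If the analysts have already seen allocation, label the comparison as added afterwards.

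The cost is a sentence or two and one 2×2 table; the class variable is already in the locked AE file. The downside is that a class comparison does not show which symptom drives a difference, which is why the term-level table stays.

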There will be no difference in mean corrected 15-F2t-isoprostane concentration or 6MWT distance, between the *RYR1*-RM and otherwise healthy individuals.

Alternative Hypothesis (H_1)

Corrected 15-F2t-isoprostane concentration will be significantly increased and 6MWT total distance will be significantly decreased in *RYR1*-RM myopathy patients when compared to otherwise healthy individuals.

2. After 30 participants complete their 2nd visit at 6 months (prior to starting study drug/placebo), disease progression will be assessed using paired t-tests to determine changes between 0 and 6-month visits for each outcome measure. For the primary outcome measures (corrected 15-F2t-isoprostane concentration and 6MWT) change between 0 and 6-month time points will be assessed. This analysis will be repeated when all 6-month visits are completed.

Null Hypothesis (H₀)

Corrected 15-F2t-isoprostane concentration and 6MWT total distance will not change significantly between 0 and 6 months in *RYR1*-RM myopathy patients.

Alternative Hypothesis (H₁)

There will be a statistically significant difference between 0 and 6-month values for corrected 15-F2t-isoprostane concentration and/or 6MWT total distance in *RYR1*-RM myopathy patients.

Intervention phase analyses (month 6 to month 12)

- Use an independent t-test (or non-parametric equivalent) to compare pre-intervention (month 6) values for demographics, urine isoprostane and six-minute walk test between NAC versus placebo groups.
- Using multiple imputation (x40 datasets and minimum/maximum value constraints from *per protocol* data) impute missing month 12 data.
- The following GLM should be run both *per protocol* and with ITT datasets.
 1. Run a general linear model comparing month 12 month corrected 15-F2t-isoprostane concentration (corrected_f2-isop_month12, corrected_f2-isop_PGF2alpha_ratio_month12) between NAC and placebo groups controlling for pre-intervention value. Run this model again controlling for established *a priori* confounders including age, sex, height, weight, BMI, smoking status, alcohol status. Variables that do not contribute significantly to the model may be removed. (Exclude RYR023, RYR024, and all healthy volunteers).

Null Hypothesis (H₀)

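### The SAP's adverse event comparison has no onset-date rule, and its RxC test, if run on events by preferred term and arm, compares only the mix of terms

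*SAP*

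**What the plan says.** Item 2 of the SAP's Adverse Event Analysis puts two questions. The first is "Were there more specific AEs (by preferred term, Column H on excel) of any kind in NAC vs. Placebo groups". The second offers the alternative answer: "Or were AEs equally distributed between groups". Two methods are named, chi-square and an exact procedure due to Fisher, the latter in these words: "extended to general RxC tables, aka the Freeman-Halton test, will be used to compare AE frequencies between NAC and Placebo groups".

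The records are limited to three IRB categories and then cut further: "Exclude HVs (healthy volunteers) and only use RYR numbers. Exclude RYR023 and RYR024". What is left is described as "For the remaining AE events (i.e. in the 3 categories delineated above) all have individual RYR IDs". No rule refers to the date of onset.

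Item 1 is a descriptive listing of AEs by arm and points to an attached mock table. Item 3 covers causality and severity in the NAC group and points to an example table. Neither attachment is in the supplied text, and item 2 cites neither. The descriptive statistics at the start of the SAP also ask for AE frequency by system organ class and preferred term, without a unit, denominator or window.

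Protocol section 4a has participants randomized at the end of the month-6 visit, after the natural history phase, and contacted once more six months after the third visit. Protocol section 17 says that the AE spreadsheet records when each event occurred.

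**The concern.** Two things are at stake.

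**Window.** A participant has about six months of follow-up before any study drug or placebo, and a contact after treatment ends. AEs from those periods cannot reflect a drug effect in the way on-drug AEs can. Counted by eventual arm, they add similar numbers to both arms and pull the comparison towards equality.

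**Test.** With two arms, an RxC extension is needed only if the other dimension has more than two categories. Item 2 names preferred term as the classifier and the data are called events, so a preferred-term-by-arm table of events is the natural layout. Such a test takes each arm's total as given and asks only whether the terms are mixed in the same proportions. A non-significant result could then be read as an equal distribution when AEs are more frequent on NAC. A significant one could come from a few participants with repeated events.

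**Working it through.** **Inputs.** The documents give no AE rates and no figure for this test, so there is no stated result to reproduce. Arm size is taken as 38, the planning target in protocol section 10b. That target rests on the superseded glutathione endpoint and serves here only as a plausible size. All AE rates below are assumed.

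**1. Dilution from the missing window.** Let the true on-drug ratio be 2 and let reporting be proportional to contacts. Section 4a gives 2 pre-drug contacts (month-1 call, month-6 visit), 7 on-drug contacts (weeks 1 and 3, months 2, 3, 4 and 5, month-12 visit) and 1 post-treatment contact. Observed ratio = (2 × on + off) / (on + off).

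| Assumption | Pre-drug events included | Post-treatment events included too |
|---|---|---|
| 2 pre, 7 on, 1 post | (14 + 2)/(7 + 2) = 1.78 | (14 + 3)/(7 + 3) = 1.70 |
| Baseline visit also counted (3 pre) | (14 + 3)/(7 + 3) = 1.70 | (14 + 4)/(7 + 4) = 1.64 |
| Equal monthly reporting (6, 6, 6) | (12 + 6)/(6 + 6) = 1.50 | (12 + 12)/(6 + 12) = 1.33 |

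This describes dilution of a rate ratio. It applies to item 1's counts by arm and to any comparison of frequency, whatever the table layout.

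**2. An even excess is invisible to a term-by-arm test.** Suppose five terms have NAC/placebo events of 20/10, 16/8, 12/6, 8/4 and 4/2. Every row has the same 2:1 split, so observed equals expected in every cell: chi-square = 0 on 4 df, p = 1.00, and Freeman-Halton p = 1.00. The totals, 60 v 30, give an exact binomial p = 0.002 under equal exposure. Tripling every term (90 v 30) still gives p = 1.00 on both RxC tests. Conversely, equal totals (35 v 35) with a different mix give p of about 0.03.

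**3. Simulation.** Eight terms have Poisson rates 0.4, 0.4, 0.3, 0.3, 0.2, 0.2, 0.1, 0.1 (sum 2.0 per placebo participant), with 38 per arm, Pearson chi-square on events and alpha 0.05. In the uneven cases three terms with rates 0.4 + 0.3 + 0.3 = 1.0 are raised, that is, half of placebo events. Paired figures are without / with strong between-person variation (gamma frailty, variance 1).

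| Comparison | Uneven excess, ratio 2 | Uneven excess, ratio 3 |
|---|---|---|
| RxC on events | 34% / 33% | 80% / 79% |
| Per-participant count, affected class (Welch) | 95% / 60% | 100% / 95% |
| Per-participant count, all AEs (Welch) | 80% / 29% | 100% / 69% |

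- With an even excess at ratios 1.5 to 3, RxC rejects in about 4–5% of trials, which is the null rate.
- With no drug effect and recurrence within person and term (gamma shape 2, 1, 0.5, 0.2), RxC rejects in 7%, 12%, 20% and 47% of trials. At shapes 0.5 and 0.2 the per-participant count tests stay near 5%.
- An overall any-AE Fisher test reaches only about 11–12% for the uneven excess at ratio 2 without frailty. At 2 AEs per participant, 1 − e⁻² = 86% of the placebo arm already has an AE, which leaves little room to differ.
- Eight separate per-term 2×2 Fisher tests with no effect give at least one p < 0.05 in about 14–19% of trials.

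**The case against.** **Layout.** The strongest point is that the layout is not fixed by the supplied text. The words about RxC tables may apply to Fisher's test alone, so 2×2 chi-squares per preferred term are not excluded. A table of participants with 0, 1 or 2+ events by arm would also be RxC and would have no mix problem. The attached mock tables, not supplied, may settle unit and denominator. This stands. A reader might infer that the plan commits to a test blind to any excess on NAC, but the documents do not support that. Even on the term-by-arm reading, the test has partial power when the excess is confined to some terms.

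**Window.** One could say that the earlier SAP heading for the intervention phase, which names months 6 to 12, implies a window. The AE analysis has its own heading, lists its own exclusions and sets no date filter, so the gap remains as written.

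**Remedy.** A participant-level analysis is not better in every form. The overall any-AE Fisher test is weaker than RxC for an uneven excess, and the total count does no better than RxC at ratio 2 under strong between-person variation (29% v 33%). The class-count advantage assumes that the affected class was named correctly in advance. These limits stand and shape the fix.

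**Consequence.** A reader might infer that a safety signal would go unseen. It would not: item 1 lists AEs by arm, protocol section 17 sends AEs to the medical monitor and the monitoring committee, and no stopping rule uses this p-value.

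**Conclusion.** The point holds in two parts of different strength. The missing onset-date rule follows directly from the text: as written, off-drug AEs enter the NAC–placebo comparison. The direction of the effect is clear. Its size (a ratio of 2 falling to about 1.6–1.8, or to 1.3–1.5 under equal monthly reporting) depends entirely on assumed reporting patterns.

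The weakness of the RxC test is conditional on an event table of preferred term by arm. On that reading the blindness to an even excess is a mathematical property and needs no assumed rates. The power and false-positive percentages do depend on assumed rates, number of terms and degree of recurrence. The overall consequence is modest, but the correction is nearly free and should be made.

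**What to change.** 1. Limit the arm comparison to AEs with onset from first dose to the month-12 visit, using the recorded dates. List other events separately.
2. State the unit, table layout and denominator for item 2.
3. For each preferred term (column H) and system organ class (column G), report participants with at least one event over participants dosed in each arm, with risk differences and confidence intervals. Label per-term 2×2 p-values as descriptive only.
4. Add a per-participant AE count or rate comparison that allows for recurrence, overall and for the gastrointestinal class named in advance. Protocol section 7 already identifies gastrointestinal symptoms as the main ones for this product. The choice of model can be left to the statistician.
5. Do not rely on an overall any-AE Fisher test. If the RxC test is kept, state that a non-significant result does not show that AEs were equally distributed.

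The cost is SAP wording and a date filter on data already held. The downsides are slightly longer tables and unadjusted per-term p-values. Item 1 can stay as a listing by arm.
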